6.5. Pooling of Centers

Analyses will not include study site as a factor in the model. Region (North America and Europe) will be included, so sites will not be pooled based on the number of subjects, but by region.

6.6. Subgroups

Subgroups to be analyzed for select endpoints include age group (children 6-12 and adolescents 13-18) and region (North America and Europe).

This document is confidential.

7. Demographic, Other Baseline Characteristics and Medication

7.1. Subject Disposition and Withdrawals

Subject disposition will be presented for all subjects, which include the following:

- Number of subjects enrolled
- Number (%) of subjects in the Safety Set
- Number (%) of subjects in the Modified Intent-to-Treat Set
- Number (%) of subjects who completed the study
- Number (%) of subjects who discontinued study prematurely and their reason

A separate by-subject listing of subject disposition and withdrawal will also be provided.

7.2. Demographic and Other Baseline Characteristics

Demographics and other baseline characteristics will be summarized for the Modified Intent-to-Treat and ITT Set. Summary statistics and by-subject listings will be provided.

Demographics and baseline characteristics will include age, sex, ethnicity, race, weight, height, body mass index (BMI).

Age at Study day 1 = (Study day 1 visit date - date of birth + 1) / 365.25 and truncated to complete years.

Height (in cm) = height (in inches) * 2.54

Weight (in kg) = weight (in lbs) * 0.4536

BMI (kg/m²) = Weight(kg)/[Height(m)²]

Demographics and baseline characteristics will also be summarized by treatment group (ecopipam, placebo and overall) from CL (EBS-101-CL-001) study.

7.3. Medical History

A summary table of the number and percentage of subjects by medical history, system organ class (SOC) and preferred term will be produced from the Safety Set. Medical history will be sorted alphabetically by SOC and in descending order of subjects per preferred term within each SOC.

Medical history will be coded using the Medical Dictionary for Regulatory Activities (MedDRA) version 22.0 or higher.

A separate by-subject listing of medical history will also be provided.

Medical History will also be summarized by treatment group (ecopipam, placebo and overall) from CL (EBS-101-CL-001) study.

This document is confidential.

7.4. Medication

All prior and concomitant medications will be summarized based on classification using the Anatomical Therapeutic Chemical (ATC) classification and preferred drug name from the World Health Organization Drug Dictionary, version Mar 2019, or later.

A separate by-subject listing of medications will also be provided.

7.4.1. Prior Medication

Prior medications are defined as medications entered in the eCRF that either start, or end before the first dose of study medication. Prior medications will be summarized by ATC level 2 and preferred drug name for the Safety Set.

Prior medications which continue after first dose of study medication will also be classified as a concomitant medication.

7.4.2. Concomitant Medication

Concomitant medications are defined as medication on the eCRF that are taken on or after or are ongoing at the start date of dosing. Concomitant medications will be summarized by ATC level 2 and preferred drug name for the Safety Set.

This document is confidential.

8. Efficacy

The mITT as well as ITT set will be used for the analysis of the efficacy endpoints.

The YGTSS, CGI-TS-S, and C&A-GTS-QOL will be assessed at Baseline, Months 1, 3, 6, 9 and 12. The CGI-TS-I will be assessed at Months 1, 3, 6, 9 and 12.

8.1. Yale Global Tic Severity Scale (YGTSS)

The YGTSS is a clinician-completed rating scale used to quantify overall tic severity as well as specific subdomains of tic number, frequency, intensity, complexity and interference. Each of these subdomains is scored, on a 5-point scale, separately for motor and vocal tics and then summed across both motor and vocal tics to yield a total tic score (TTS) ranging from 0 to 50. The YGTSS also provides for an overall impairment rating (0 = “none” to 50 = “severe”). Global YGTSS (YGTSS-GS) is the total of YGTSS-TTS and impairment score (YGTSS-I). Efficacy will be analyzed for the YGTSS-TTS, YGTSS-I and YGTSS-GS.

The observed YGTSS-TTS along with motor and phonic subdomains, YGTSS-I and YGTSS-GS values and their changes from baseline will be summarized by visit. The paired t-test will be used for analyzing the change from baseline within treatment.

The percent of subjects with a 25% or greater improvement on the YGTSS-TTS score at any time between the Baseline visit and post-baseline visit will be considered as a Response. Any subject who has at least 1 Response (>=25% improvement) will be considered as a Responder; otherwise, the subject will be considered a Non-Responder. Responder and Non-Responder will be summarized at each post-baseline visit and overall.

YGTSS-TTS will also be summarized by treatment group (ecopipam, placebo and overall) from CL (EBS-101-CL-001) study.

All YGTSS data will be presented in a listing.

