3.2. Secondary Objective(s)

The secondary objective of this study is to evaluate the durability of effect of ecopipam in pediatric subjects (aged ≥ 6 to ≤ 18 years at Baseline of the EBS-101-CL-001 study) with TS.

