4.1. Efficacy Endpoints

- Changes in the Yale Global Tic Severity Scale – Total Tic Score (YGTSS-TTS) from baseline to Months 1, 3, 6, 9, 12.
- Changes in the Yale Global Tic Severity Scale – Impairment (YGTSS-I) and Global (YGTSS-TTS + YGTSS-I = YGTSS-GS) from baseline to Months 1, 3, 6, 9, 12.
- Changes in Clinical Global Impression of Tourette Syndrome of Severity (CGI-TS-S) from Baseline to Months 1, 3, 6, 9, 12.
- Clinician Global Impression Tourette Syndrome of Improvement (CGI-TS-I) at Months 1, 3, 6, 9, 12.
- Changes in Gilles de la Tourette Syndrome—Quality of Life Scale for Children and Adolescents (C&A-GTS-QOL) from Baseline to Months 1, 3, 6, 9, 12.

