6.4. Visit Windows

The following visit windows will be used in the summarization or analysis of safety laboratory, vital signs, ECG, and physical exam data. If more than 1 data point falls within the window, then the data point

This document is confidential.

closest to the target day will be used. If there are 2 data points equidistant to the target day, one high and one low, then the high data point will be used. Visit windowing will not be applicable to follow-up visits.

If Baseline is Day 1, then:

Month 1 (target day = 29) 2 - 42

Month 2 (target day = 57) 43 - 70

Month 3 (target day = 85) 71 - 98

Month 4 (target day = 113) 99 - 126

Month 5 (target day = 141) 127 - 154

Month 6 (target day = 169) 155 - 182

Month 7 (target day = 197) 183 - 210

Month 8 (target day = 225) 211 - 238

Month 9 (target day = 253) 239 - 266

Month 10 (target day = 281) 267 - 294

Month 11 (target day = 309) 295 - 322

Month 12 (target day = 337) 323 and above (and not a follow-up visit)

For all efficacy and safety scales a modified last observation carried forward (LOCF) approach will be used to reassign Early Termination visits. Early Termination visits will be assigned to the next scheduled visit (per Schedule of Assessments for the parameter) after a subjects' latest scheduled visit before early termination.

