9.9. COVID-19 Analyses

Due to COVID-19 pandemic, additional analyses will be conducted:

- Listings of COVID-19 related study disruptions by subject and by site, including descriptions of the disruption.
- Protocol deviations due to COVID-19 will be summarized by type in a table.

This document is confidential.

10. Changes from Analysis Planned in Protocol

As per protocol, the Modified Intention-to-Treat (mITT) set was defined as all subjects who receive at least one dose of study drug which is same as the safety population set. Hence the mITT set definition was updated as 'all subjects who receive at least one dose of study drug and have at least one post Baseline scoring of YGTSS'.

Following updates and additional analysis were included in the SAP after the data base lock.

- An additional analysis set, Intention-to-Treat (ITT) Set, was defined as all enrolled subjects. All efficacy analysis will also be conducted using the ITT population.
- Visit windowing will be used in the summarization or analysis of safety laboratory, vital signs, ECG, and physical exam data.
- For all efficacy and safety scales a modified last observation carried forward (LOCF) approach will be used to reassign Early Termination visits. Early Termination visits will be assigned to the next scheduled visit (per Schedule of Assessments for the parameter) after a subjects' latest scheduled visit before early termination.
- Demographics and baseline characteristics will also be summarized by treatment group (ecopipam, placebo, overall) from CL (EBS-101-CL-001) study in the mITT Set (Table 14.1.3.1a), and be also summarized for the ITT Set (Table 14.1.3.1b).
- Medical history will also be summarized by treatment group (ecopipam, placebo, overall) from CL (EBS-101-CL-001) study in the Safety Set (Table 14.1.3.2a).
- Extent of exposure summary by days will be provided as well (Table 14.1.5a).
- YGTSS-TTS will also be summarized by treatment group (ecopipam, placebo and overall) from CL (EBS-101-CL-001) study (Tables 14.2.1.1.1a).
- Efficacy summaries for the ITT Set will be generated (Tables 14.2.1.1.1b, 14.2.1.1.2b, 14.2.1.1.3b, 14.2.1.1.4b, 14.2.1.2b, 14.2.1.3b, and 14.2.1.4b).
- A summary of the percent of subjects with a 25% or greater improvement on the YGTSS-TTS in mITT set will be provided (Table 14.2.1.1.5).
- A summary of the most common ($\geq 5\%$) AEs first onset by month will be provided in Table 14.3.1.9.1 and by month (new incidence or ongoing) in Table 14.3.1.9.2.

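### The overall YGTSS-TTS responder row is an ever-responder rate that relapse cannot lower, and no planned output estimates the within-subject change from an early on-treatment visit to Month 12, although durability is the secondary objective

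*SAP*

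**What the plan says.** SAP 3.2 gives the secondary objective as to "evaluate the durability of effect of ecopipam in pediatric subjects". The first efficacy endpoint in SAP 4.1 is the change in "Total Tic Score (YGTSS-TTS) from baseline to Months 1, 3, 6, 9, 12". SAP 6.2 defines Baseline as the last value before the first open-label dose, and defines change only against that value. SAP 8.1 plans by-visit summaries and one test: "The paired t-test will be used for analyzing the change from baseline within treatment".

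SAP 8.1 also defines a responder summary. An improvement of 25% or more "at any time between the Baseline visit and post-baseline visit will be considered as a Response". Then: "Any subject who has at least 1 Response (>=25% improvement) will be considered as a Responder; otherwise, the subject will be considered a Non-Responder". The display is described as follows: "Responder and Non-Responder will be summarized at each post-baseline visit and overall". No confirmation, persistence or loss-of-response rule is given.

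The responder summary is not among the SAP 4.1 endpoints. SAP Section 10 lists it with the items added after database lock: "A summary of the percent of subjects with a 25% or greater improvement on the YGTSS-TTS in mITT set will be provided" (Table 14.2.1.1.5).

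For subjects who leave early, SAP 6.4 says: "Early Termination visits will be assigned to the next scheduled visit (per Schedule of Assessments for the parameter"), meaning the visit that follows the subject's latest scheduled visit. The score is not carried on to Month 12.

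**The concern.** Durability asks whether an effect seen early on treatment is still there later. The overall responder row cannot answer that. Each of the five post-baseline YGTSS visits gives a subject another chance to qualify, and none can take the status away. A subject who improves at Month 1 and is back at Baseline from Month 3 onwards counts the same as one who holds the improvement for a year.

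The test against pre-dose Baseline shows whether scores at a visit differ from those before dosing. It does not show how much of the early change was kept. Comparing the Month 3 and Month 12 means by eye is possible, but the two means can come from different subjects. A subject who leaves after Month 3 has the Early Termination score placed at Month 6 and is absent at Month 12.

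At stake is the reading of the secondary objective. The one response figure that covers the whole study could stay high while the effect fades.

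**Working it through.** **What the outputs contain.** I compared the objective with SAP 4.1, 6.2 and 8.1 to 8.3, the table, listing and figure indexes (SAP 14 to 16), and protocol 13.2.2.

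- Change from Baseline by visit, with a paired t-test: planned for YGTSS-TTS, impairment, global score, CGI-TS-S and quality of life.
- CGI-TS-I by visit, YGTSS-TTS by parent-study arm (Table 14.2.1.1.1a) and subject listings (16.2.6.1 and 16.2.6.1b): planned.
- Responders by visit and overall: planned.
- Within-subject change from any on-treatment visit to Month 12, share of early responders still responding, or time to loss of response: not found.
- Figures over time: quality of life, its VAS and growth z-scores, but not YGTSS.

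**How far the overall row can move.** The documents give no responder rate or sample size for this analysis, so there is no stated figure to reproduce. What follows is an illustration only.

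Inputs from protocol 5.2.2.1 (PSY302, a 4-week crossover study with a different regimen): baseline 32.8, ecopipam Day 30 change −5.6 (SD 8.7), placebo Day 30 SD 5.8. The last is used as an alternative SD.

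Assumptions not in the documents: normal changes, fixed baseline, no dropout, visits at Months 1, 3, 6, 9 and 12, and a common within-subject correlation ρ of 0.3 to 0.7 (0.9 shown for sensitivity).

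Threshold: 0.25 × 32.8 = 8.2 points. Response at a visit with mean change μ is Φ((−8.2 − μ)/SD):

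- SD 8.7, μ = −5.6: Φ(−2.6/8.7) = Φ(−0.299) = 38%. μ = 0: Φ(−8.2/8.7) = Φ(−0.943) = 17%.
- SD 5.8, μ = −5.6: Φ(−2.6/5.8) = Φ(−0.448) = 33%. μ = 0: Φ(−8.2/5.8) = Φ(−1.414) = 8%.

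The ever-rate was simulated with 400,000 subjects per case: change at visit k = μₖ + SD × (√ρ·z + √(1−ρ)·eₖ), and a subject is a Responder if any of the five changes is −8.2 or lower. Full fade means μ = −5.6, −4.2, −2.8, −1.4, 0.

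| SD | ρ | Stable −5.6 | Full fade | Fall (points) | No mean change at any visit |
|---|---|---|---|---|---|
| 8.7 | 0.3 | 80.5% | 68.8% | 11.7 | 50.9% |
| 8.7 | 0.5 | 72.8% | 61.4% | 11.4 | 44.1% |
| 8.7 | 0.7 | 64.3% | 53.5% | 10.8 | 36.8% |
| 8.7 | 0.9 | 52.8% | 44.1% | 8.7 | 27.6% |
| 5.8 | 0.3 | 74.7% | 56.1% | 18.6 | 28.2% |
| 5.8 | 0.5 | 66.9% | 49.8% | 17.1 | 24.2% |
| 5.8 | 0.7 | 58.1% | 43.3% | 14.8 | 19.7% |
| 5.8 | 0.9 | 46.7% | 36.3% | 10.4 | 14.2% |

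The fall that does occur comes from fewer first responses at later visits, not from subjects losing the status. With SD 8.7 and ρ of 0.3 to 0.7, 68 to 75% of overall-row Responders under full fade would not meet 25% at Month 12. The figure is 41 to 53% even when the effect is stable, because of visit-to-visit variation.

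**What a within-subject contrast would give.** From Month 3 to Month 12 the expected change is 0 if stable and 0 − (−4.2) = +4.2 under full fade. Under half fade (−5.6 to −2.8 in equal steps) it is −2.8 − (−4.9) = +2.1. The 95% CI half-width is t × 8.7 × √(2(1−ρ))/√n. For ρ = 0.3, 0.5 and 0.7 and assumed n:

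- n = 40: 3.29, 2.78, 2.16
- n = 60: 2.66, 2.25, 1.74
- n = 100: 2.04, 1.73, 1.34

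**The case against.** The strongest reply is that waning is already visible. By-visit responder rows, read as status at the visit, would fall from 38% to 17% in the illustration. By-visit changes, CGI scores, the table by parent-study arm and the listings all add to that. The Month 12 test against Baseline does answer whether improvement is present at one year, and the documents do not define durability as Month 12 against an earlier visit. The study is single-arm, has no sample-size basis, and is described in the protocol synopsis as descriptive. The responder table is not a listed endpoint, and its timing is disclosed in Section 10.

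Most of this stands, and it limits the point. A reader might infer that the plan is blind to loss of effect. The documents do not support that, because the by-visit outputs can show it. A reader might also infer that the by-visit responder rows are cumulative. The 'at any time' wording allows that, but status at the visit is the more natural reading, so this is an ambiguity and not an established fault. Nor do the documents present the overall row as the measure of durability.

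Two further objections also stand. How little the overall row moves depends on the assumed SD and correlation. And the proposed contrast keeps only subjects with both scores, so it does not remove the problem of early leavers.

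What the reply does not meet is that none of these outputs estimates, with an interval, how much of the early on-treatment change the same subjects kept.

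**Conclusion.** The point holds in a limited form. By its definition the overall row is an ever-responder rate that relapse cannot lower, so it does not measure durability. That rests on the SAP wording alone. No planned output estimates the within-subject change from an early on-treatment visit to Month 12, and visit means can come from different subjects.

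The size is illustrative, at correlation 0.3 to 0.7. Under full fade the ever-rate falls 11 to 12 points and stays at 53 to 69% with SD 8.7. With SD 5.8 it falls about 15 to 19 points and stays at 43 to 56%. With no mean change at any visit it is still 37 to 51% or 20 to 28% respectively. These figures borrow 4-week data from another study and assume normality and no dropout. They show how the row behaves and do not predict this study's results.

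This affects how the secondary objective is read, not a powered test. The change should be made because it is cheap and gives durability a direct estimate.

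**What to change.** 1. In SAP 8.1, state that by-visit response means a reduction of at least 25% from Baseline at that visit, and show the denominator.
2. Label the overall row 'ever responder, post hoc' and do not use it as evidence of durability.
3. Add the within-subject Month 3 to Month 12 change in YGTSS-TTS with n and a 95% CI, marked post hoc and read as an estimate, not a test. Month 3 is the first YGTSS visit after the 4-week titration and the Month 1 visit. Use scheduled Month 12 scores, state whether Early Termination scores reassigned to Month 12 under SAP 6.4 are included, and show the result both ways. At an assumed 40 to 100 subjects and SD 8.7 the half-width is about 1.3 to 3.3 points, so a half fade of 2.1 points may not be resolved.
4. Beside it, give the Month 3 mean change for subjects with and without a Month 12 score. As a sensitivity analysis, add a Month 12 responder rate with missing counted as non-response.

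The cost is SAP wording and one or two tables from data already collected. Three limits should be stated with the results. The contrast is chosen after lock. It covers only subjects with both scores, so it is likely to favour durability if subjects leave for inadequate therapeutic effect, a reason listed in protocol 7.5. Without a control arm it cannot separate durability of the drug effect from the natural course of tics, which protocol 5.1 describes as variable and declining with age.

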8.2. Clinician Global Impression Tourette's Syndrome of Improvement & Severity (CGI-TS-I & S)

The CGI consists of 2 reliable and valid 7-item Likert scales used to assess severity and change in clinical symptoms. The scale ranges from 1 = “very much improved” to 7 = “very much worse” for the CGI-TS-I. The CGI severity scale (CGI-TS-S) will be used at each study site visit and ranges from 1 = “Normal, not ill at all” to 7 = “Extremely ill.”

The CGI-TS-S will be assessed at Baseline, Months 1, 3, 6, 9 and 12. The observed CGI-TS-S values and their changes from baseline will be summarized by visit. The paired t-test will be used for analyzing the change from baseline within treatment.

The CGI-TS-I will be assessed at Months 1, 3, 6, 9, and 12. The observed CGI-TS-I values will be summarized by visit.

All CGI-TS-I and CGI-TS-S data will be presented in a listing.

8.3. Gilles de la Tourette Syndrome—Quality of Life Scale for Children and Adolescents (C&A-GTS-QOL)

C&A-GTS-QOL is a patient-reported health related quality of life measure developed for children and adolescents. Versions of the scale appropriate for subjects 6-12 years of age and 13-18 years of age will

This document is confidential.

be provided. Subjects who turn 13 during the course of the study should continue to be assessed using the version of the scale initially administered.

The C&A-GTS-QOL is a 27-item questionnaire specific to TS patients that asks the patient to assess the extent to which their quality of life is impacted by their symptoms. The C&A-GTS-QOL contains 6 subscales (cognitive, coprophenomena, psychological, physical, obsessive-compulsive, and activities of daily living (ADL)) and uses a 5 point Likert scale ranging from no problem to extreme problem. Patients will also be asked how satisfied they feel overall with their life at that moment by using a Visual Analogue Scale (VAS) between 0 and 100 (Su et al 2017). Following are the questions assessed in each C&A GTS QOL subscale:

- Cognitive (questions 11, 12, 13, 14, 18, 20, 21, 23) (range: 0- 32)
- Psychological (questions 15, 16, 17, 19, 25, 27) (range: 0 – 24)
- Obsessive-compulsive (questions 7, 8, 9, 10) (range: 0 – 16)
- Physical (questions 1, 3, 4) (range: 0 – 12)
- Coprophenomena (questions 5, 6, 22) (range: 0 -12)
- ADL (questions 2, 24, 26) (range: 0-12)

Scores for the six subscales are generated by summing items and, for ease of interpretation, transformation to a range of 0 to 100 ($100 \times [(observed\ score - min\ possible\ score) / (max\ possible\ score - min\ possible\ score)]$). The total score, resulting from the sum of the subscale scores, is also normalized to a 0–100 range. For C&A GTS-QOL, if a response to 1 question is missing within the subscale, the missing response will be replaced with the average of the remaining responses within the subscale; if responses to 2 or more questions within a subscale are missing, the missing responses will not be replaced and the subscale score will be set to missing; if at least 1 subscale is missing then the total score will be set to missing. For all analysis and summary, transformed scores will be used.

Summary statistics for the overall VAS score, QOL subscale scores for Cognitive, Psychological, Obsessive-compulsive, Physical, Coprophenomena, and ADL and QOL total score will be presented along with a full data listing by visit. The paired t-test will be used for analyzing the change from baseline within treatment. Mean C&A-GTS-QOL Change from Baseline Total Score and VAS Change from Baseline Score Over Time will be illustrated in a figure.

This document is confidential.

9. Safety

The population used for safety analyses will be the Safety Set (SS). Study Visits may be completed in locations other than clinic and/or safety and efficacy assessments required at these visits will be made available for remote administration due to restrictions as a consequence of the COVID-19 pandemic or other qualifying event. Safety will be monitored throughout the study at all visits by repeated monitoring of adverse events (AEs), vital signs, the Columbia-Suicide Severity Rating Scale (C-SSRS), the Abnormal Involuntary Movement Scale (AIMS), the Barnes Akathisia Rating Scale (BARS), the Pediatric Anxiety Rating Scale (PARS) and Children's Depression Rating Scale-Revised (CDRS-R). In addition to these assessments, at Baseline, Months 1, 3, 6, 9 and 12 safety will also be monitored by clinical and laboratory evaluations and electrocardiogram (ECG) monitoring. At the Follow Up visit, AE monitoring, the C-SSRS, clinical and laboratory evaluations and vital signs will be assessed. Laboratory evaluations will include hematology, chemistry, urine values and HbA1c. A Follow Up phone call will be conducted 30 days after the last dose of study medication to assess AEs. Subjects will be monitored for signs of abuse, and withdrawal or dependence. Additional assessments (all visits except the follow up visit) will include the AIMS, the BARS, the CDRS-R and the PARS. C-SSRS will also be assessed (all visits including the Follow Up visit).

All safety data will be summarized in Safety Set.

